6.5. Subject Withdrawal

Subjects may withdraw from the study at any time at their own request, or they may be withdrawn at any time at the discretion of the investigator or sponsor for safety (see also the Withdrawal From the Study Due to Adverse Events section) or behavioral reasons, or the inability of the subject to comply with the protocol-required schedule of study visits or procedures at a given study site.

If a subject does not return for a scheduled visit, every effort should be made to contact the subject. All attempts to contact the subject and information received during contact attempts must be documented in the subject's medical record. In any circumstance, every effort should be made to document subject outcome, if possible. The investigator should inquire about the reason for withdrawal, request that the subject return for a final visit, if applicable, and follow up with the subject regarding any unresolved AEs.

If the subject withdraws from the study, and also withdraws consent for disclosure of future information, no further evaluations should be performed, and no additional data should be collected. The sponsor may retain and continue to use any data collected before such withdrawal of consent.

Subjects who withdraw after randomization will not be replaced.

Lost to follow-up:

All reasonable efforts must be made to locate subjects to determine and report their ongoing status. Lost to follow-up is defined by the inability to reach the subject after a minimum of 2 documented phone calls, faxes, or emails as well as lack of response by the subject to 1 registered mail letter. All attempts should be documented in the subject's medical records. If it is determined that the subject has died, the site will use locally permissible methods to obtain the date and cause of death. The site staff and representative may consult publicly available sources, such as public health registries and databases, in order to obtain updated contact information. If, after all attempts, the subject remains lost to follow-up, then the last-known-alive date as determined by the investigator should be reported and documented in the subject's medical records.

7. ASSESSMENTS

Every effort should be made to ensure that the protocol-required tests and procedures are completed as described. However, it is anticipated that from time to time there may be circumstances outside of the control of the investigator that may make it unfeasible to perform the test. In these cases, the investigator will take all steps necessary to ensure the safety and well-being of the subject. When a protocol-required test cannot be performed, the investigator will document the reason for this and any corrective and preventive actions that he or she has taken to ensure that normal processes are adhered to as soon as possible. The study team will be informed of these incidents in a timely manner.

For samples being collected and shipped, detailed collection, processing, storage, and shipment instructions and contact information will be provided to the investigator site prior to initiation of the study.

7.1. Biological Samples

Samples will be used only for scientific research. Each sample will be labeled with a code so that the laboratory personnel testing the samples will not know the subject's identity. Samples that remain after performing assays outlined in the protocol may be stored by Pfizer. Unless a time limitation is required by local regulations or ethical requirements, the samples may be stored for up to 20 years after the end of the study and then destroyed. If allowed by the ICD, stored samples may be used for additional testing to better understand the safety profile and/or immune responses to the vaccine(s) under study in this protocol, to inform the development of other products, and/or for vaccine-related assay work supporting vaccine programs. CCI

The subject may request that his or her samples, if still identifiable, be destroyed at any time; however, any data already collected from those samples will still be used for this research. The biological samples may be shared with other researchers as long as confidentiality is maintained.

7.2. Immunogenicity

Blood samples will be collected as detailed in [Section 6](#):

Primary Study Cohort - Stage 1: The total volume of blood collected from each subject will be approximately 225 mL over the course of the 1-year study. An additional approximately 300 mL will be collected from consenting PBMC subjects for the exploratory cellular analysis endpoints. The total volume of blood collected from subjects at these sites will be approximately 525 mL over the 1-year study period.

Primary Study Cohort - Stage 2: The additional blood volume collected from each subject participating in the revaccination stage is approximately 125 mL.

At PBMC collection sites, approximately 250 mL will be collected from consenting PBMC subjects for the exploratory cellular analysis endpoints. The total volume of blood collected from subjects at these sites will be approximately 375 mL during Stage 2.

RSV Vaccine Month-0, Month-2 Cohort: The total volume of blood collected from each subject will be approximately 150 mL over the course of the 1-year study.

At PBMC collection sites, approximately 450 mL will be collected from consenting PBMC subjects for the exploratory cellular analysis endpoints. The total volume of blood collected from subjects at these sites will be approximately 600 mL over the 1-year study period.

CCI

Whole blood will be taken for isolation of PBMCs for further research into the immune response (eg, B cells, plasmablasts, T cells).

Sample collection, processing, storage, and shipping information can be found in the study reference manual (SRM) or equivalent manual. All assays will be performed at Pfizer Vaccine Research & Development located at [name] and/or at a facility designated by Pfizer.

7.2.1. RSV and Influenza Vaccine Antibody Testing

Sera collected will be assayed for RSV A– and RSV B–neutralizing antibody levels, anti-RSV prefusion F IgG levels, and immunoglobulin levels against nonvaccine RSV antigens. RSV A– and RSV B–neutralizing antibody levels will be determined for each blood sample and reported as the neutralizing titer. IgG levels will be determined against both RSV A and RSV B vaccine prefusion F antigens in a direct-binding Luminex immunoassay (dLIA) and reported as an anti-RSV prefusion F IgG antibody titer. Immunoglobulin levels against nonvaccine RSV antigens will also be tested by dLIA.

Hemagglutination inhibition antibody titers will be measured by the standard hemagglutination inhibition assay (HAI) for the influenza vaccine strains contained in the vaccine. H3N2-neutralizing antibody titers will also be investigated. Testing will be performed by a facility designated by Pfizer.

7.2.2. Exploratory Assays, Immunogenicity Assessments, and Assay Development

PBMCs isolated from whole blood will be used for evaluation of cellular immune responses to the RSV vaccine formulations. Exploratory analyses may include characterization of B-cell, plasmablast, and T-cell immune responses, and repertoire analyses.

A subset of subjects will be included in the whole blood collection procedural requirements for the exploratory cellular analysis endpoints for this study. The subset will be determined at the site level; specifically, those sites that have access to the appropriate specimen-processing laboratories will provide all subjects for the subset. It is anticipated that the subjects from the selected sites will constitute approximately 1/3 of the total number of randomized subjects.

Sera and plasma remaining after completion of the planned immunologic assays from blood draws taken throughout the study may be used for additional vaccine and infectious disease-related research, including exploratory immunologic assays for further characterization of the vaccine response.

CCI

7.3. Safety Parameters

Safety parameters will be assessed as described in the [Schedule of Activities](#) and below.

A medical history and physical examination will be performed on all subjects, to establish a baseline. Significant medical history and observations from the physical examination will be documented in the CRF.

The safety parameters include e-diary reports of local reactions and systemic events that occur in the 14 days after investigational product administration at each vaccination visit. These prospectively collected occurrences of local reactions and systemic events are graded as described in [Section 7.3.1](#).

In the Primary Study Cohort - Stage 1, the first 4 subjects vaccinated in the study must be observed by blinded site staff for any acute reactions for at least 4 hours after vaccination. Vaccination of subjects will be limited to a maximum of 6 subjects per day during the first week of enrollment (up to 30 vaccinated subjects in total) to maintain safety oversight.

For subjects enrolled, thereafter, irrespective of study cohort, blinded site staff must observe subjects for any acute reactions for at least 30 minutes after investigational product administration. Acute reactions after investigational product administration will be assessed and documented.

In addition, AEs, medically attended AEs (MAEs), AEs of specific interest, and SAEs are collected, recorded, and reported as defined in [Section 8](#). An MAE is defined as a nonserious AE that results in an evaluation at a medical facility.

7.3.1. Subject Electronic Diary

The subject will be asked to monitor and record local reactions (left arm), systemic events, fever, and antipyretics/pain medication used to treat symptoms, each evening for 14 days following each vaccination visit (Day 1 through Day 14, where Day 1 is the day of vaccination). The e-diary allows recording of these assessments only within a fixed time window, thus providing the accurate representation of the subject's experience at that time. Data on local reactions, systemic events, and antipyretics/pain medication used to treat symptoms recorded in the e-diary will be transferred electronically to the e-diary vendor, where they will be available for review by investigators, their qualified designees, and sponsor staff at all times via an internet-based portal. At intervals agreed to by the vendor and Pfizer, these data will be transferred electronically to Pfizer for analysis and reporting. These data do not need to be recorded by the investigator in the CRF. However, if a subject withdraws because of prompted events recorded in the e-diary, the event(s) should be recorded on the AE page of the CRF, regardless of whether the investigator considers the event(s) to be clinically significant.

Investigators (or appropriately qualified designee) are required to review the e-diary data online to evaluate subject compliance and as part of the ongoing safety review (see Stopping Rules in [Section 7.4](#)).

The investigator or designee must obtain stop dates for any reactions ongoing on the last day that the e-diary was completed. The stop dates should be documented in the source documents and the information entered in the CRF.

7.3.2. Grading Scales

The grading scales used in this study to assess local reactions and systemic events (including fever) described in Tables 4 through 6 below are derived from the Food and Drug Administration (FDA) Center for Biologics Evaluation and Research (CBER) guidelines on toxicity grading scales for healthy adult volunteers enrolled in preventive vaccine clinical trials.¹¹

7.3.3. Local Reactions

Following each vaccination visit (Day 1 through Day 14, where Day 1 is the day of vaccination), subjects will be asked to assess redness, swelling, and pain at the injection site (left arm) and to record the symptoms in the e-diary in the evening. Subjects will also record any peeling/scaling (exfoliative dermatitis) or blackening of the skin (necrosis), at the injection site on the left arm.

Redness and swelling will be measured and recorded in measuring device units (range: 1 to 20, and ≥ 21) and then categorized during analysis as mild, moderate, or severe based on the grading scale in [Table 7](#) below. Measuring device units can be converted to centimeters according to the following scale: 1 measuring device unit = 0.5 cm.

A subject with severe redness, swelling, or pain or any peeling/scaling (exfoliative dermatitis) or blackening of the skin (necrosis) at the injection site on the left arm will be prompted to contact the investigator to perform an unscheduled visit to assess the reaction. If the subject does not call the investigator, the site should call the subject.

Only an investigator is able to classify a subject's local reaction as Grade 4, after clinical evaluation of the subject or documentation from another medically qualified source (eg, emergency room or hospital record), or, in the case of pain at the injection site only, contact with the subject. If a subject experiences a Grade 4 local reaction, the investigator must immediately notify the sponsor. Grade 4 reactions will be collected as an AE on the CRF. The event will be graded using the AE severity grading scale ([Section 8.3](#)).

Site staff will educate the subject regarding signs and symptoms that would prompt site contact. The procedure for notification of the sponsor is provided in the study documentation.

If a local reaction persists beyond the end of the e-diary period, the subject will be requested to report that information and/or any new AEs that develop to the investigator. The investigator will enter this additional information in the subject's source notes and CRF.

Table 7. Grading Scale for Local Reactions

	Mild Grade 1	Moderate Grade 2	Severe Grade 3	Grade 4^a
Redness	2.5 cm to 5.0 cm (5 to 10 measuring device units)	>5.0 cm to 10.0 cm (11 to 20 measuring device units)	>10 cm (>20 measuring device units)	Necrosis or exfoliative dermatitis
Swelling	2.5 cm to 5.0 cm (5 to 10 measuring device units)	>5.0 cm to 10.0 cm (11 to 20 measuring device units)	>10 cm (>20 measuring device units)	Necrosis
Pain (at the injection site)	Does not interfere with activity	Interferes with activity	Prevents daily activity	Emergency room visit or hospitalization for severe pain at the injection site

- a. Grade 4 assessment should be made by the investigator using the AE severity grading scale. The assessment will be collected on the AE case report form.

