- Assess any systemic events (fatigue, headache, nausea, vomiting, diarrhea, muscle pain, or joint pain) that are present in accordance with the reactogenicity grading scale provided in [Section 7.3.4](#).
- Ask the subject if he/she attended an emergency room visit or was hospitalized.
- For severe pain at the injection site on the left arm associated with an emergency room visit or hospitalization, severe systemic events, associated with an emergency room visit or hospitalization, or any necrosis or exfoliative dermatitis, the investigator must assess these events in accordance with the severity AE grading scale provided in [Section 8](#) for documentation on the AE CRF.
- Complete the source documents.
- The investigator or an authorized designee completes the CRFs.

Subjects will be instructed to contact the site to report any significant illness, medically attended event, or hospitalization that occurs during the study period.

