8.2.3. Serious Adverse Events

A serious adverse event is any untoward medical occurrence at any dose that:

- Results in death;
- Is life-threatening (immediate risk of death);
- Requires inpatient hospitalization or prolongation of existing hospitalization;
- Results in persistent or significant disability/incapacity (substantial disruption of the ability to conduct normal life functions);
- Results in congenital anomaly/birth defect.

Or that is considered to be:

- An important medical event.

Medical and scientific judgment is exercised in determining whether an event is an important medical event. An important medical event may not be immediately life-threatening and/or result in death or hospitalization. However, if it is determined that the event may jeopardize the subject or may require intervention to prevent one of the other AE outcomes, the important medical event should be reported as serious.

Examples of such events are intensive treatment in an emergency room or at home for allergic bronchospasm; blood dyscrasias or convulsions that do not result in hospitalization; or development of drug dependency or drug abuse.

Medical device complaints may meet the SAE reporting requirement criteria (see the Medical Device Complaint Reporting Requirements section). An incident is any malfunction (ie, the failure of a device to meet its performance specifications or to perform as intended; performance specifications include all claims made in the labeling for the device) that, directly or indirectly, might lead to or might have led to the death of a subject, or user, or of other persons, or to a serious deterioration in their state of health.

A serious injury that can cause a serious deterioration in state of health can include:

- A life-threatening illness, even if temporary in nature;
- A permanent impairment of a body function or permanent damage to a body structure;
- A condition necessitating medical or surgical intervention to prevent the above 2 bulleted items;

Examples: clinically relevant increase in the duration of a surgical procedure; a condition that requires hospitalization or significant prolongation of existing hospitalization;

- Any indirect harm as a consequence of an incorrect diagnostic or in vitro diagnostic device test results when used within the manufacturer's instructions for use;
- Fetal distress, fetal death, or any congenital abnormality or birth defects.

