8.3. Severity Assessment

GRADE	If required on the AE page of the CRF, the investigator will use the adjectives MILD, MODERATE, SEVERE, or LIFE-THREATENING to describe the maximum intensity of the AE. For purposes of consistency, these intensity grades are defined as follows:	
1	MILD	Does not interfere with subject's usual function.
2	MODERATE	Interferes to some extent with subject's usual function.
3	SEVERE	Interferes significantly with subject's usual function.
4	LIFE-THREATENING	Life-threatening consequences; urgent intervention indicated.

Note the distinction between the severity and the seriousness of an AE. A severe event is not necessarily an SAE. For example, a headache may be severe (interferes significantly with the subject's usual function) but would not be classified as serious unless it met one of the criteria for SAEs, listed above.

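### The SAP's maximum-severity displays have no route for investigator-confirmed Grade 4 reactions, so these appear at Grade 3 or lower; the protocol's Grade 4 footnote also needs clearer wording

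*Protocol*

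**What the plan says.** **Grade 4 in the protocol.** Tables 7 and 8 (Sections 7.3.3 and 7.3.4) define Grade 4 by specific events. For redness it is necrosis or exfoliative dermatitis, and for swelling it is necrosis. For pain it is "Emergency room visit or hospitalization for severe pain at the injection site", and the seven systemic events in Table 8 have matching wording. Footnote a under both tables says that the "Grade 4 assessment should be made by the investigator using the AE severity grading scale". On that scale (Section 8.3) Grade 4 reads "Life-threatening consequences; urgent intervention indicated".

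**Body text.** Section 7.3.3 lets only an investigator classify a subject's "local reaction as Grade 4, after clinical evaluation of the subject or documentation from another medically qualified source", or, for pain, after contact with the subject. The reaction is then collected as an AE, and "The event will be graded using the AE severity grading scale". Section 7.3.4 does the same for systemic events. For emergency-room, hospital, necrosis and exfoliative dermatitis cases, Section 6.4 says that "the investigator must assess these events in accordance with the severity AE grading scale", for the purpose of the AE CRF. Under stopping rule 2 (Section 7.4), one Grade 4 reaction judged possibly related pauses the study.

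**Analysis.** Section 7.3.3 says that redness and swelling are "categorized during analysis as mild, moderate, or severe based on the grading scale" in Table 7. SAP 3.1.1 takes redness, swelling and pain from the e-diary. SAP 3.1.1.2 takes the highest grade over Days 1 to 14 from those answers, and SAP 3.1.2 handles systemic events in a similar way. The footnotes to SAP Tables 4 and 6 add that Grade 4 is on the AE CRF and so does not come from the diary. SAP 6.1.1 and 6.1.2 make maximum severity the primary display and repeat it in stacked bar charts.

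**The concern.** The SAP's severity tables print a Grade 4 column, and the derivation asks for the highest grade, yet no data path leads to Grade 4. A programmer following the text would use diary values only. Under the protocol, subjects also record skin blackening and peeling in the diary, but the SAP derivations cover only redness, swelling and pain. The most severe local signs on the plan's own scale therefore have no place in the reactogenicity display.

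The grade shown for such a subject then depends on the size of the redness or swelling and not on the confirmed finding. These displays report primary endpoints, and SAP 7.2 says the interim results help to choose dose and formulation.

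The footnote raises a second, smaller question. Read literally, it replaces the table criteria with a life-threatening threshold, and stopping rule 2 does not say which definition it uses.

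**Working it through.** No figure in the plan bears directly on this point, so the check applies the plan's own rules to example cases.

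**1. Highest grade the diary can produce.** From Protocol 7.3.3 and SAP Table 4, 1 measuring unit is 0.5 cm. For redness and swelling, 5 to 10 units is Grade 1, 11 to 20 is Grade 2, and more than 20 is Grade 3. Diary values run from 1 to 20, plus a category for 21 or more. Over all of these the highest derivable grade is 3.

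**2. Confirmed necrosis, by largest redness in the diary.**

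| Largest redness | Size | Grade in Protocol Table 7 | Grade derived from the diary |
|---|---|---|---|
| 4 units | 4 × 0.5 = 2.0 cm | 4 | 0 (no redness) |
| 8 units | 8 × 0.5 = 4.0 cm | 4 | 1 (mild) |
| 21 units or more | more than 10 cm | 4 | 3 (severe) |

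The first row uses SAP 3.1.1.3, which treats redness or swelling below 2.5 cm as no reported reaction. That statement stands in the duration section; carrying it over to maximum severity is the natural reading.

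**3. How many Grade 4 cells are affected.** Table 7 has 3 and Table 8 has 7, so 10 in all. The emergency-room or hospital criterion fills 1 + 7 = 8 of them. These concern a symptom that is already severe, so if the diary agrees they appear at Grade 3 and lose only the distinction between 3 and 4. The other 2 cells, redness and swelling, can appear anywhere from Grade 0 to Grade 3. Fever is analysed by temperature range and is not affected.

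**4. Any severe local reaction on a given day (SAP Table 5).** This is yes if any of redness, swelling or pain is severe that day. A subject with necrosis is therefore a no only if none of the three diary reactions is severe that day. Likewise, maximum severity of any local reaction takes the worst of the three.

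**5. Size in one group.** Protocol Table 4 gives about 31 per group. Assume one confirmed necrosis with small redness and no other severe redness. The intervals are Clopper-Pearson 95%, the method in SAP 5.2.1.

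- SAP as written, redness of Grade 3 or higher: 0/31 = 0%. The upper limit is 1 − 0.025^(1/31) = 0.1122, so the interval is 0% to 11.2%.
- With Grade 4 included: 1/31 = 3.2%. The lower limit is 1 − 0.975^(1/31) = 0.0008 and the upper limit is 0.1670, so the interval is 0.1% to 16.7%.

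**6. The footnote and the stopping rules.** Life-threatening events and hospital admissions both meet the seriousness criteria in Section 8.2.3, so if possibly related they already trigger stopping rule 1. The choice of definition therefore changes rule 2 only for related, non-serious reactions: emergency-room visits without admission, necrosis, or exfoliative dermatitis.

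**The case against.** **The separation is deliberate, and the event is not lost.** Both statements are correct. The SAP footnotes place Grade 4 on the AE CRF on purpose, and keeping subject-reported and investigator-reported data apart is a legitimate choice. Within the AE window the event appears by SOC and PT in SAP 6.1.4, which is itself a primary-endpoint analysis. A reader might infer that the worst reactions vanish from the report; the documents do not support that. What remains is that the reactogenicity display gives a lower grade than the plan's own scale, with no planned note. A necrosis given mild or moderate intensity under Section 8.3 would also be outside the severe-AE summary.

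**The unseen specifications may deal with it.** SAP Section 2 says that mock-ups and programming rules are prepared separately. A note or merge rule may exist there. That the tables stop at Grade 3 is an inference from the SAP text, and it should be checked against those files.

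**The footnote is resolved elsewhere.** This largely stands. Sections 6.4, 7.3.3 and 7.3.4 support two steps: classify by the table criterion, then record the Section 8.3 intensity on the CRF. The literal reading would make rule 2 nearly redundant with rule 1, which also favours two steps. A reader might infer that stopping rule 2 cannot be operated. The documents do not support that: any Grade 4 reaction must be notified to the sponsor at once, and unblinded sponsor personnel decide whether a rule is met.

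**The size is hypothetical.** This is true. The two intervals overlap heavily, and the documents give no rate for such reactions.

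**Conclusion.** The point holds as a minor one. As the SAP is written, an investigator-confirmed Grade 4 reaction is shown at Grade 3 at most in the primary maximum-severity tables and bar charts. Necrosis or exfoliative dermatitis with small redness can be shown as mild or as no redness. In a group of 31, one such case moves redness of Grade 3 or higher from 1/31 to 0/31. This rests on three assumptions: the programming follows the SAP text, no other subject in the group has severe redness, and at least one such case occurs. The number of cases cannot be estimated from the documents.

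No analysis is invalidated. The footnote is loose wording and not an operative contradiction. No change in the chance of a study pause can be calculated from it, because the documents give no event rates.

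**What to change.** (a) In SAP 3.1.1.2, 3.1.2, 6.1.1 and 6.1.2, add investigator-confirmed Grade 4 reactions from the AE CRF (Days 1 to 14) as a category in the maximum-severity tables and stacked bars. Add a table note that Grades 1 to 3 come from the e-diary and Grade 4 from the investigator.

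(b) Reword footnote a under Protocol Tables 7 and 8: a reaction that meets the Grade 4 criterion in the table, as confirmed by the investigator, counts as Grade 4 for stopping rule 2, and its Section 8.3 intensity is recorded separately on the AE CRF.

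The cost is one sentence in the protocol, one severity category and one table note. No endpoint, sample size or data collection changes. The downside is that one table then mixes diary and investigator data, which the note makes plain. Change (b) affects only vaccinations still to come; Stage 1 finished enrolling in June 2019, before Amendment 3. Change (a) can still serve the final analysis of every cohort.
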